5.1. Overall Design

Study I9N-MC-FCAB (FCAB) is a Phase 2, multicenter, randomized, double-blind, placebo-controlled, parallel-group, outpatient study evaluating the efficacy and safety of LY3375880 SC 600 mg Q4W, 150 mg Q4W, and 50 mg Q4W as compared to placebo Q4W in adult subjects with moderate-to-severe AD. In addition, LY3375880 300mg Q4W will be evaluated in the maintenance period as described below.

The study duration will be up to 65 weeks over 4 study periods:

- Period 1: Screening Period lasting from 8 to 35 days prior to Week 0 (baseline, Visit 2).
- Period 2: Induction Period, lasting from Week 0 (baseline, Visit 2) through Week 16 (Visit 8).
- Period 3: Maintenance Period, lasting from Week 16 (Visit 8) through Week 52 (Visit 17, inclusive). At Week 16, the following will occur:
 - Responders (defined as having achieved a 50% reduction in the Eczema Area and Severity Index score [EASI-50] response, regardless of whether rescue therapy has been initiated) will undergo the following re-randomizations:
 - Subjects on any dose of LY3375880 will be re-randomized at a 2:1 ratio to either maintain their current regimen or to receive placebo until loss of response (not achieving a 25% reduction in the EASI score [EASI-25] at a scheduled visit), at which point they will restart their induction period regimen.
 - Subjects on placebo will continue receiving placebo until loss of response, at which point they will be reassigned to receive LY3375880 at 300 Q4W.
 - Nonresponders will undergo the following reassessments:
 - Subjects on 50 mg Q4W will be reassigned to 150 mg Q4W.
 - Subjects on 150 mg Q4W will be reassigned to 300 mg Q4W.
 - Subjects on 600 mg Q4W will remain on their current regimen.
 - Subjects on placebo will be reassigned to receive 300 mg Q4W.
 - Subjects with persistent disease activity, defined as not achieving EASI-25 for 3 consecutive scheduled maintenance period visits, not already on 600 mg Q4W will be reassigned to 600 mg Q4W for the remainder of the study.
- Period 4: Post-Treatment Follow-Up Period, spanning approximately 8 weeks from Week 52 (after Visit 17) to Week 60 (Visit 801).

Rescue therapy is permitted starting at Week 8 for subjects who do not achieve an EASI-25 response. Refer to Section [7.7.3](#) for details.

Treatment Arms and Duration:

[figure not shown]

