5.4. Scientific Rationale for Study Design

Study FCAB is the first clinical trial evaluating the safety and efficacy of LY3375880 in subjects with moderate-to-severe AD. A moderate-to-severe subject population is appropriate for a novel investigational product (IP) with immunomodulating properties. Three active dose levels of LY3375880 to evaluate the primary endpoint will allow the evaluation of safety and efficacy across a broad dose range to fully characterize the benefit/risk profile of LY3375880 and provide information on dose selection in future studies. A double-blind, placebo-controlled design limits bias for both subject and investigator assessments and enables a clearer interpretation of active drug effect.

The treatment period includes an induction and maintenance period. The induction period of the study is designed to evaluate the primary endpoint, which is the proportion of subjects achieving IGA of 0 or 1 with a ≥ 2 -point improvement at Week 16. The IGA is a global disease severity scale that is widely used in AD trials, and is accepted by the FDA as a primary endpoint for trials conducted for approval of new drugs (Futamura et al. 2016; Simpson et al. 2016). A time point at Week 16 to evaluate the primary endpoint is appropriate, based on previous clinical trials of systemic therapies in AD (Simpson et al. 2016). A maintenance period spanning Weeks 16 to 52 allows for an evaluation of safety and efficacy over a longer duration. In addition to the dose regimens being tested in the induction period, an additional dosing regimen of 300mg Q4W will be evaluated during the maintenance period to obtain safety and efficacy data of an intermediate dose. Given the broad dose range being evaluated in this study, data regarding this dose will further aid in exposure-response modeling and dose selection for future studies. During the maintenance period, subjects taking LY3375880 who respond to study drug at Week 16 will be re-randomized to either maintain their current regimen or administered placebo until disease recurrence to understand durability of disease response. This information will provide the dose

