- Period 4: Post-Treatment Follow-Up Period, spanning approximately 8 weeks from Week 52 (Visit 17) to Week 60 (Visit 801).

Approximately 200 subjects will be randomized 1:1:1:1 at Week 0 to 1 of 4 treatment groups: placebo SC (Q4W), LY3375880 SC 600 mg (Q4W), LY3375880 150 mg (Q4W), or LY3375880

50 mg (Q4W). The study duration will be up to 65 weeks (Screening Period: Up to 5 weeks; Induction Period: 16 weeks; Maintenance Period: 36 weeks; Follow-up Period: 8 weeks).

Subjects will be stratified at randomization according to disease severity (IGA [3 versus 4]) and geographic region (Japan versus Rest of World).

Figure FCAB.4.1 illustrates the study design. The blinding procedure is described in the Protocol.

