## **5.13. Safety Analyses**

The general methods used to summarize safety data, including the definition of baseline value are described in Section 5.2.2.

Safety analyses will include data after rescue, unless otherwise stated, and patients will be analyzed according to the investigational product to which they were randomized at Week 0 (Visit 2). Additional analyses may be conducted using data after rescue to systemic therapy for some safety topics such as systemic treatment-emergent adverse events (TEAEs), and serious adverse events (SAEs). Safety analyses will take place using the safety population defined in Section 5.2.1.

Safety topics that will be addressed include the following: AEs, clinical laboratory evaluations, vital signs and physical characteristics, Columbia Suicide Severity Rating Scale (C-SSRS), the Self-Harm Supplement Form, safety in special groups and circumstances, including adverse events of special interest (AESI) (see Section 5.13.5), and investigational product interruptions.

Unless otherwise specified, by-visit summaries will include planned on-treatment visits. For tables that summarize events (such as AEs, categorical lab abnormalities, shift to maximum value), post-last dose follow-up data will be included. Follow-up data is defined as all data occurring up to 30 days (planned maximum follow-up time) after last dose of treatment including rescue, regardless of study period except for deaths and malignancies. For deaths and

malignancies, all available follow-up data up to the end of the study will be included. Listings will include all safety data.

For selected safety assessments, descriptive statistics may be presented for the last measure observed during post-treatment follow-up (up to 30 days after the last dose of treatment including rescue, regardless of study period).

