### **5.13.2. Adverse Events**

Adverse events are recorded in the eCRFs. Each AE will be coded to system organ class (SOC) and preferred term (PT) using the Medical Dictionary for Regulatory Activities (MedDRA) version that is current at the time of database lock. Severity of AEs is recorded as mild, moderate, or severe.

A TEAE is defined as an event that either first occurred or worsened in severity after the first dose of study treatment and on or prior to the last visit date during the analysis period. The analysis period is defined as the treatment period plus 30 days off-drug follow-up time, except for deaths and malignancies for which the analysis period includes the treatment period and off-drug follow-up time.

Adverse events are classified based upon the MedDRA PT. The MedDRA Lowest Level Term (LLT) will be used in defining which events are treatment-emergent. The maximum severity for each LLT during the baseline period up to first dose of the study medication will be used as baseline. If an event with missing severity is preexisting during the baseline period, and persists during the treatment period, then the baseline severity will be considered mild for determining TEAE (that is, the event is treatment-emergent if the severity is coded moderate or severe postbaseline and not treatment-emergent if the severity is coded mild postbaseline). If an event occurring postbaseline has a missing severity rating, then the event is considered treatment-emergent. The day and time for events where onset is on the day of the first dose of study treatment will both be used to distinguish between pretreatment and posttreatment in order to derive treatment-emergence. Should there be insufficient data for AE start date to make this comparison (for example, the AE start year is the same as the treatment start year, but the AE start month and day are missing), the AE will be considered treatment-emergent.

In an overview table, the number and percentage of subjects who experienced a TEAE or serious adverse event (SAE), died due to an AE, or discontinued from study due to an AE will be summarized by treatment.

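### The SAP labels 30 days the planned maximum follow-up, but both documents plan 8 weeks, so Week 60 safety data from completers fall outside the by-arm event tables

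*SAP*

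**What the plan says.** SAP section 5.13 includes off-drug data in tables that summarise events, such as adverse events, categorical laboratory abnormalities and shifts to maximum. It limits them thus: "Follow-up data is defined as all data occurring up to 30 days (planned maximum follow-up time) after last dose of treatment including rescue". The rule applies whatever the study period. Deaths and malignancies are exempt, and listings include all safety data.

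SAP section 5.13.2 carries the same limit into the definition of a treatment-emergent adverse event (TEAE): "The analysis period is defined as the treatment period plus 30 days off-drug follow-up time", again with deaths and malignancies exempt. It adds that the event must have occurred "on or prior to the last visit date during the analysis period".

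The planned follow-up is longer. Protocol section 5.1 has "Post-Treatment Follow-Up Period, spanning approximately 8 weeks from Week 52 (after Visit 17) to Week 60 (Visit 801", and SAP section 4.1 gives the same period in almost the same words. In the protocol's Schedule of Activities the last injection is at Visit 17 and the only later visit is Visit 801. At that visit adverse events, chemistry, haematology, urinalysis and antidrug antibodies are all collected.

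Other SAP safety sections use other windows. Section 5.13.3 builds laboratory shift tables for the Induction and Maintenance Periods. Section 5.13.6.2 does the same for creatinine shifts, and tabulates treatment-emergent creatinine abnormalities in a Dosing Period that is not defined. Section 5.13.2.1 counts serious events in a study drug period that is not defined either.

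**The concern.** A figure presented as the planned maximum follow-up is about half of what the trial plans and collects. A programmer who follows the SAP will drop from the by-arm TEAE tables any non-fatal, non-malignancy event that starts more than 30 days after the last dose. The registry count of other (non-serious) events follows, because SAP section 5.18 requires such an event to be a TEAE. A reader of the report would be told that 30 days was all the follow-up there was.

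The omitted interval has some safety interest. Protocol section 3.3 commits to close monitoring for events plausibly related to immunogenicity. SAP section 5.13.5 tabulates treatment-emergent antibodies with no 30-day limit, so an antibody conversion found at Week 60 would be tabulated while an adverse event starting that week would not. Visit 801 also carries the only scheduled urinalysis after Week 32.

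The windows also disagree among themselves. Section 5.13 brings off-drug data into shift tables, while sections 5.13.3 and 5.13.6.2 confine those tables to treatment periods. Correcting the 30 days alone would therefore still leave Visit 801 laboratory results out.

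**Working it through.** **Inputs** (protocol section 2, Schedule of Activities)
- Last injection: Visit 17, Week 52, Day 364 ±4.
- Only post-treatment visit: Visit 801, Week 60, Day 420 ±5.
- Urinalysis: screening and Weeks 0, 16, 32 and 60.
- Limit under test: 30 days after last dose (SAP sections 5.13 and 5.13.2).

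**Planned follow-up**
- Nominal: 420 − 364 = 56 days = 8.0 weeks. This reproduces the 8 weeks in both documents.
- Shortest: (420 − 5) − (364 + 4) = 415 − 368 = 47 days.
- Longest: (420 + 5) − (364 − 4) = 425 − 360 = 65 days.
- If the last dose was instead at Week 48 (Day 336 ±4): 420 − 336 = 84 days, range 415 − 340 = 75 to 425 − 332 = 93.

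No variant gives 30 days, so the SAP's label cannot be reproduced.

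**Does Visit 801 fall in the window?** (Week 52 dose taken, no rescue)
- The window closes at 364 + 30 = Day 394, or at the latest 368 + 30 = Day 398.
- The earliest allowed Visit 801 is Day 415, and 415 − 398 = 17 days too late.
- Scheduled follow-up visits inside the window: 0 of 1.

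**Share of planned off-drug time outside the TEAE tables**
- Nominal: (56 − 30)/56 = 26/56 = 46%.
- With tolerances: 17/47 = 36% to 35/65 = 54%.

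**Why the restriction to completers without rescue.** Section 5.13 counts from the last treatment including rescue, so continued rescue moves the cut-off later. Subjects who stop study drug early stay on the visit schedule (protocol section 8.1.1), so scheduled visits can fall within 30 days of their last dose.

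**The last-visit clause.** Between Day 364 and Day 394 no visit is scheduled. An event that starts 20 days after the last dose lies inside the 30 days, but after the last scheduled visit in the analysis period. Sections 5.13 and 5.13.2 can then be read differently for the same event.

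**Context only.** If the 24-day average Phase 1 half-life (protocol section 3.2) applies here, 30 days is 30/24 = 1.25 half-lives and 56 days is 56/24 = 2.33.

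**The case against.** The best defence is that a 30-day TEAE window is a legitimate choice and that nothing disappears. Listings hold all safety data, including the hypersensitivity listing in SAP section 5.13.6.4. Registry counts of serious events do not depend on the TEAE definition, and the overview table in section 5.13.2 does not require a serious event to be a TEAE. The late tables would also say little about cause: by Week 52 many subjects have been re-randomized or reassigned, yet "patients will be analyzed according to the investigational product to which they were randomized at Week 0 (Visit 2". All of this stands. It limits the point to description and rules out any claim of harm to the Week 16 comparison. It does not make the label true, and a listing gives no counts or percentages by arm.

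Some stronger readings are tempting but not supported:
- **The last-visit clause captures no off-drug time.** That would empty the 30-day extension in section 5.13.2 of meaning, and it fails as soon as there is an unscheduled visit. It shows only a clause that needs tidying.
- **Two clocks run for early stoppers.** This needs the protocol's design rationale, "The treatment period includes an induction and maintenance period", to override the term off-drug in section 5.13.2. That term points to a clock that starts when the drug stops, as in section 5.13.
- **Fatal serious events lose their exemption in section 5.13.2.1.** That section says only that fatal events count among the serious ones.
- **The tables of discontinuation due to adverse events (section 5.13.2.2) are cut short.** Nobody can stop treatment after it has ended.
- **The laboratory box plots in section 5.13.3 conflict with section 5.13.** They are continuous summaries, outside the event-table rule.
- **An output is left empty.** Section 5.13 allows a summary of "the last measure observed during post-treatment follow-up (up to 30 days after the last dose of treatment including rescue, regardless of study period"), but only as an option for selected assessments.

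**Conclusion.** The point holds, with high confidence for the label and the visit arithmetic. The SAP's planned maximum of 30 days contradicts the 8 weeks in both documents. For completers who took the Week 52 dose and are not using rescue, Visit 801 always falls outside the window, by at least 17 days. About 26 of 56 planned off-drug days (46%; 36% to 54% with visit tolerances) are missing from the by-arm TEAE tables and from the registry count of other events. Visit 801 laboratory results, including the last urinalysis, are missing from the event and shift tables. The last-visit clause and the two undefined periods add ambiguity.

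This assumes visits within their tolerances and the injection schedule as printed. The documents give no basis for the number of events or subjects affected. A reader might infer that safety data are lost or that late toxicity would be hidden. The documents do not support that: listings, deaths, malignancies, antibody summaries, registry counts of serious events and ongoing blinded safety review still cover the period. This is a reporting fault that should be corrected before the tables are programmed.

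**What to change.** 1. In SAP section 5.13, delete or correct the words that call 30 days the planned maximum follow-up time.
2. Keep 30 days for TEAEs, and add descriptive by-arm tables of adverse events from day 31 after the last dose to Week 60 and of Visit 801 laboratory shifts, including urinalysis. Alternatively, extend the event window through Visit 801; 65 days after the last dose would cover the visit tolerances.
3. In section 5.13.2, remove the last-visit bound or align it with the chosen window.
4. Define the study drug period (section 5.13.2.1) and the Dosing Period (section 5.13.6.2) to match section 5.13, and state in sections 5.13.3 and 5.13.6.2 whether off-drug results enter the shift tables.

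The cost is wording in a few SAP sections and, under the first option, a few extra tables. No new data are collected. The added tables are shown by Week 0 arm after re-assignment, so they should be labelled descriptive. Extending the window instead would bring some off-drug background events into the TEAE counts.

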### **5.13.1. Extent of Exposure**

Duration of exposure (in days) to study drug will be summarized for the safety population in the Induction Period and for the maintenance population in the Maintenance Period by treatment group using descriptive statistics (n, mean, SD, minimum, 1st quartile, median, 3rd quartile, maximum).

For subjects without drug interruption, the duration of exposure for each patient is the date of last dose – date of first dose +1. If subjects have drug interruption, the duration of exposure for each patient is the (Treatment end date before drug interruption – date of first dose +1) + (date of last dose – treatment re-start date +1).

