Study I9N-MC-FCAB (FCAB) is a Phase 2, multicenter, randomized, double-blind, placebo-controlled, parallel-group, outpatient study evaluating the efficacy and safety of LY3375880 subcutaneous (SC) 600 mg every 4 weeks (Q4W), 150 mg Q4W, and 50 mg Q4W as compared to placebo Q4W in adult subjects with moderate-to-severe AD. In addition, LY3375880 300mg Q4W will be evaluated during the maintenance period.

The study duration will be up to 65 weeks over 4 study periods:

- Period 1: Screening Period, lasting 8 to 35 days prior to Week 0 (baseline, Visit 2).
- Period 2: Induction Period, lasting from Week 0 (baseline, Visit 2) through Week 16 (Visit 8).
- Period 3: Maintenance Period, lasting from Week 16 (Visit 8) through Week 52 (Visit 17, inclusive).
- Period 4: Post-Treatment Follow-Up Period, lasting 8 weeks from Week 52 (after Visit 17) to Week 60 (Visit 801).

Treatment Arms and Duration:

Subjects will be randomized 1:1:1:1 at Week 0 to 1 of 4 treatment groups: placebo SC Q4W, LY3375880 SC 600 mg Q4W, LY3375880 150 mg Q4W, or LY3375880 50 mg Q4W. The study duration will be up to 65 weeks (Screening Period: Up to 5 weeks; Induction Period: 16 weeks; Maintenance Period: 36 weeks; Post-Treatment Follow-up Period: 8 weeks).

Number of Subjects:

Approximately 200 subjects will be randomized.

Statistical Analysis:

Efficacy will be conducted on the intent-to-treat population. Safety analyses will be conducted on the safety population.

Treatment comparisons of discrete efficacy variables between LY3375880 and placebo will be made using a logistic regression analysis with treatment, baseline disease severity (Investigator's Global Assessment [IGA] [3 versus 4]), and geographic region in the model. Treatment comparisons of the continuous efficacy variables will be made using a mixed-effects model of repeated measures (MMRM) analysis with treatment, baseline disease severity, geographic region, visit, and treatment-by-visit interaction as fixed categorical effects and, if a baseline score is available, baseline score and baseline score-by-visit interaction as fixed continuous effects. All tests of treatment effects will be conducted at a 2-sided alpha level of 0.05, with no control for multiple comparisons.

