Fisher's exact test will be used for the adverse events (AEs), discontinuations, and other categorical safety data for between-treatment group comparisons. Continuous vital signs, body weight, and other continuous safety variables including laboratory variables will be analyzed by an analysis of covariance with treatment and baseline value in the model.

2. Schedule of Activities

Table FCAB.1. I9N-MC-FCAB Schedule of Activities

	Screening	Induction Period								Maintenance Period								Posttreatment Follow-Up
		Period 1				Period 2				Period 3								
Visit Number	1	2	3	4	5	6	7	8	9	10	11	12	13	14	15	16	17	801
Weeks from randomization		0	1	2	4	8	12	16	20	24	28	32	36	40	44	48	52 or ET	60
Days from randomization		0	7	14	28	56	84	112	140	168	196	224	252	280	308	336	364	420
Visit tolerance interval (days)	-8 to -35		±2	±2	±2	±4	±4	±4	±4	±4	±4	±4	±4	±4	±4	±4	±4	±5
Procedure																		
Inclusion and exclusion review	X	X																
Informed consent	X																	
Clinical assessments																		
Demographics	X																	
Medical history	X																	
Previous and current AD treatments	X																	
Weight		X																
Height		X																
Vital signs (BP and Pulse)	X	X	X	X	X	X	X	X	X	X	X	X	X	X	X	X	X	X
Complete physical examination	X																	
Symptom-directed physical examination ^a		X	X	X	X	X	X	X	X	X	X	X	X	X	X	X	X	X
Adverse events		X	X	X	X	X	X	X	X	X	X	X	X	X	X	X	X	X
Concomitant medication	X	X	X	X	X	X	X	X	X	X	X	X	X	X	X	X	X	X
ePRO (patient diary) dispensed	X	X		X	X	X	X	X	X	X	X	X	X	X	X	X	X	

	Screening	Induction Period								Maintenance Period								Posttreatment Follow-Up
		Period 1				Period 2				Period 3								
Visit Number	1	2	3	4	5	6	7	8	9	10	11	12	13	14	15	16	17	801
Weeks from randomization		0	1	2	4	8	12	16	20	24	28	32	36	40	44	48	52 or ET	60
Days from randomization		0	7	14	28	56	84	112	140	168	196	224	252	280	308	336	364	420
Visit tolerance interval (days)	-8 to -35		±2	±2	±2	±4	±4	±4	±4	±4	±4	±4	±4	±4	±4	±4	±4	±5
ePRO (patient diary) returned		X		X	X	X	X	X	X	X	X	X	X	X	X	X	X	X
Randomization		X						X ^b										
IWRS entry	X	X	X	X	X	X	X	X	X	X	X	X	X	X	X	X	X	X
IP SC injections		X			X	X	X	X	X	X	X	X	X	X	X	X	X	
Investigator Scales																		
IGA ^c	X	X		X	X	X	X	X	X	X	X	X	X	X	X	X	X	X
EASI ^c	X	X		X	X	X	X	X	X	X	X	X	X	X	X	X	X	X
SCORAD ^c	X	X		X	X	X	X	X	X	X	X	X	X	X	X	X	X	X
Health Outcome Measures and Other Questionnaires																		
POEM ^{c,d}	X	X		X	X	X	X	X	X	X	X	X	X	X	X	X	X	X

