LY3375880 has been tested in humans in the Phase 1 study I9N-MC-FCAA (FCAA). Single doses ranging from 3 mg to 400 mg SC and 100 mg and 700 mg intravenous (IV); and multiple doses of 150 mg SC, 300 mg IV and 700 mg IV, were administered to healthy volunteers. No dose-limiting AEs were observed and dose escalation to the maximum dose of 700mg IV was achieved. As of 06 September 2018, no deaths, serious adverse events (SAEs), or discontinuations due to AEs were reported. Based on analysis of data from single-dose administration between 3 mg to 400 mg SC and 100 mg IV, the average half-life was 24 days.

Study I9N-MC-FCAB (FCAB) is the first Phase 2 study for LY3375880 and will evaluate the safety and efficacy of LY3375880 in adults with moderate-to-severe AD. Results from this study will lead to further development of LY3375880 in AD and other related diseases.

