7.1. Treatments Administered

The study involves a comparison of each LY3375880 dosing regimen (600 mg, 300 mg in Maintenance period, 150 mg, and 50 mg SC Q4W) with placebo. [Table FCAB.4](#) shows the treatment regimens. Subcutaneous LY3375880 should be administered as 3 to 4 injections (maximum volume: 2 mL per injection) preferably in the abdomen in separate quadrants, whenever possible. All subjects should be monitored after dosing according to investigator practice or local standard of care. Detailed instructions for IP administration will be provided separately by the sponsor.

Table FCAB.4. Treatment Regimens

Treatment Name	LY3375880	Placebo
Dosage Formulation	LY3375880 for clinical trial use supplied as solution in vial, manufactured to contain 200 mg/2 mL of LY3375880 (100 mg/mL)	0.9% Sodium chloride
Dosage Levels	600 mg SC Q4W, 300 mg SC Q4W (In Maintenance period only) 150 mg SC Q4W, 50 mg SC Q4W	NA
Route of Administration	SC injection(s)	SC injection(s)

Abbreviations: NA = not applicable; Q4W = every 4 weeks; SC = subcutaneous.

The investigator or designee is responsible for:

- explaining the correct use of the IP to the site personnel.
- verifying that instructions are followed properly.
- maintaining accurate records of IP dispensing and collection.
- at the end of the study returning all unused medication to Lilly, or its designee, unless the sponsor and sites have agreed all unused medication is to be destroyed by the site, as allowed by local law.

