### 5.2. General Considerations

This plan describes *a priori* statistical analyses for efficacy, health outcomes, and safety that will be performed.

Statistical analysis of this study will be the responsibility of Eli Lilly and Company (Lilly). The statistical analyses will be performed using SAS® Version 9.4 or higher.

Not all displays described in this SAP will necessarily be included in the clinical study report (CSR). Not all displays will necessarily be created as a “static” display. Some may be incorporated into interactive display tools instead of or in addition to a static display. Any display described in this SAP and not included in the CSR would be available upon request.

For continuous measures, summary statistics will include sample size, mean, standard deviation (SD), minimum, median, and maximum. The 1st quartile and 3rd quartile may also be presented. The minimum and maximum will be reported to the same number of decimal places as the raw data recorded in the database. The mean, 1st quartile, median, 3rd quartile, and SD will generally be reported to 1 more decimal place than the raw data recorded in the database. In general, the maximum number of decimal places reported shall be 4 for any summary statistic. For categorical measures, summary statistics will include the sample size, frequency count, and percentage. Percentages will be presented to 1 decimal place unless otherwise stated.

Percentages will not be presented for zero counts. Incidence rates and 95% confidence interval (CI) will be displayed for select safety endpoints.

Statistical tests of treatment effects and CIs will be performed at a 2-sided significance level of 0.05, unless otherwise stated.

All p-values will be rounded up to 3 decimal places. For example, any p-value strictly greater than 0.049 and less than or equal to 0.05 will be displayed as 0.050. This guarantees that on any printed statistical output, the unrounded p-value will always be less than or equal to the displayed p-value. A displayed p-value of 0.001 will always be understood to mean  $\leq 0.001$ . Likewise, any p-value displayed as 1.000 will be understood to mean  $> 0.999$  and  $\leq 1$ .

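### SAP 5.13.1 ends exposure on the day of the last 4-weekly injection, so a fully dosed Induction subject is reported with 85 of 112 days and a one-dose subject with 1 day

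*SAP*

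**What the plan says.** SAP 5.13.1 gives two rules for exposure in days. For a subject with no interruption, "the duration of exposure for each patient is the date of last dose – date of first dose +1". For a subject with one, it is a sum of two parts: "Treatment end date before drug interruption – date of first dose +1) + (date of last dose – treatment re-start date +1". The result "will be summarized for the safety population in the Induction Period and for the maintenance population in the Maintenance Period by treatment group". Neither document credits any time after the final injection. The SAP does not define the treatment end date in the second rule. It also does not say whether the first dose in the Maintenance summary means the first maintenance dose.

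Dosing is 4-weekly (Protocol 7.1: "Q4W = every 4 weeks"). In the Protocol's Schedule of Activities the row "IP SC injections" is marked at Weeks 0, 4, 8 and 12, then every 4 weeks from Week 16 to Week 52. The Protocol synopsis gives the period lengths as "Induction Period: 16 weeks; Maintenance Period: 36 weeks".

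The SAP is not consistent on where the Week 16 injection belongs. SAP 5.2.2.2 expects the initial Maintenance dose at Week 16, SAP 5.9 leaves Week 16 out of the Induction dose count, and SAP 5.2.1 has subjects entering Maintenance at Week 16. SAP 4.1 runs Induction through Week 16 inclusive and starts Maintenance at Week 20.

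**The concern.** Last dose minus first dose plus one suits a tablet taken daily. With an injection every 4 weeks it leaves out the whole interval that follows the last dose. Protocol 3.2 reports from Phase 1 that "the average half-life was 24 days", so a subject is still exposed well after the injection day. The SAP's own event windows recognise this: SAP 5.13 and 5.13.2 count events up to 30 days after the last dose. A one-dose subject can therefore contribute about a month of events while being credited with 1 day of exposure.

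At stake is the Induction exposure table in the study report: its mean, quartiles, median and minimum. A further effect is possible but not established. SAP 5.2 says "Incidence rates and 95% confidence interval (CI) will be displayed for select safety endpoints" without naming a denominator. If this duration served as that denominator, the rates would be too high.

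**Working it through.** The documents state no expected exposure total, so there is no planned figure to reproduce. The check is date arithmetic.

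**Inputs**
- Induction injections on Days 0, 28, 56 and 84; further injections on Days 112 to 364 every 28 days (Schedule of Activities).
- Induction 16 × 7 = 112 days; Maintenance 36 × 7 = 252 days (Protocol synopsis).
- Comparator: 28 days credited per dose. This convention is an assumption, because the documents do not state one. It agrees with the period length, since 4 × 28 = 112.

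**No interruption, Week 16 dose counted in Maintenance**

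| Induction doses | SAP rule | 28 days per dose | Shortfall | Share counted |
|---|---|---|---|---|
| 1 | 0 − 0 + 1 = 1 | 28 | 27 | 3.6% |
| 2 | 28 − 0 + 1 = 29 | 56 | 27 | 51.8% |
| 3 | 56 − 0 + 1 = 57 | 84 | 27 | 67.9% |
| 4 | 84 − 0 + 1 = 85 | 112 | 27 | 75.9% |

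With the ±4-day window on the Week 12 visit, the four-dose figure ranges from 81 to 89 days.

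**The periods do not add up.** Taking the first maintenance dose as the start, Maintenance gives 364 − 112 + 1 = 253 days. Then 85 + 253 = 338. The same formula run once from first to last dose gives 364 − 0 + 1 = 365. The missing 27 days are Days 85 to 111, although no dose was missed.

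**Week 16 dose counted in Induction (SAP 4.1).** Induction becomes 112 − 0 + 1 = 113 days, so a completer shows no shortfall against the 112-day period. Maintenance from Week 20 (Day 140) gives 364 − 140 + 1 = 225. The total is again 113 + 225 = 338; the uncounted days move to Days 113 to 139.

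**Maintenance completers.** The rule gives 253 days against a 252-day period. Crediting 28 days to the Week 52 dose would give 280; capping at Day 364 leaves 253.

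**Interruption.** Suppose the treatment end date means the last injection before the gap. A subject who misses only Week 4 scores (0 − 0 + 1) + (84 − 56 + 1) = 30 days, against 3 × 28 = 84.

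**Drug remaining.** Under simple one-phase decay, 0.5^(28/24) = 0.445, so about 45% of the post-dose amount remains 28 days later.

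**Rates, only if this duration were the denominator.** 50 fully dosed subjects give 50 × 85/365.25 = 11.6 patient-years instead of 50 × 112/365.25 = 15.3. The inflation is 112/85 = 1.32-fold.

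**The case against.** The best defence is that this is a convention rather than an arithmetic error, and that it touches one descriptive table. Much of that stands, and it rules out several stronger readings.

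- *A reader might infer that exposure is understated throughout the trial.* Maintenance completers already score 253 days against 252. Unless exposure is meant to run beyond Week 52, nothing is lost there.
- *A reader might infer that arms are biased against each other.* For uninterrupted subjects followed at least 28 days after the last dose, the loss is 27 days whatever the arm, so absolute differences in mean exposure largely survive. Early stoppers are worst hit in relative terms only.
- *A reader might infer that safety rates will be inflated.* No section specifies a patient-year rate. Adverse events are reported as percentages of subjects and compared by Fisher's exact test (SAP 5.2.3, 5.13.2), and those results do not change. The 1.32-fold figure depends on a denominator that the SAP does not state.
- *A reader might infer that every interruption loses an interval per segment.* That rests on one reading of an undefined treatment end date.
- The 28 days for a one-dose subject is a maximum. Someone who leaves the study on Day 10 could be credited with at most 10 − 0 + 1 = 11 days. However, Protocol 8.1.1 keeps subjects who stop study drug in the study unless there is a reason to leave it.
- The half-life shows that exposure outlasts the injection day. It does not yield 28 days, and it says nothing about placebo.

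The defence does not rescue the rule. It leaves 27 days of continuous dosing in neither period on either placement of the Week 16 dose, and it credits a single 4-weekly injection with 1 day.

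**Conclusion.** The rule as written gives a materially wrong Induction exposure table. Fully dosed subjects appear with 85 of 112 days (24% low), two-dose subjects with 29 instead of 56, and one-dose subjects with 1 instead of up to 28. A subject who misses only Week 4 may appear with 30 instead of 84, depending on what the treatment end date means.

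The figures rest on on-time dosing, 28 days credited per dose and the Week 16 injection counted in Maintenance. If SAP 4.1 governs, Induction completers show 113 days, but the errors for early stoppers and the gap between periods remain.

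The documents do not support a claim of biased arm comparisons, altered adverse event tests or established rate inflation, and no efficacy result is involved. The point should be corrected before the exposure tables are produced.

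**What to change.** Replace the formula in SAP 5.13.1. For each continuous dosing segment (a run of scheduled injections with none missed), take the earliest of:
- the last dose date in the segment + 27 days;
- the day before the first dose of the next segment or period;
- the date of death or study exit.

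Subtract the first dose date in the segment, add 1, and sum the segments. This gives 28, 56, 84 and 112 days for one to four on-time Induction doses. For the subject who misses only Week 4 it gives 28 + 56 = 84 days.

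In the same edit:
- define the treatment end date before an interruption as the last injection before the gap;
- say that the Maintenance summary starts from the first maintenance dose, and whether it is capped at Week 52 or runs into follow-up;
- name the denominator of the incidence rates in SAP 5.2;
- reconcile the Week 20 start of Maintenance in SAP 4.1 with Week 16 in SAP 5.2.1, 5.2.2.2 and 5.9.

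The cost is a short SAP revision and the matching program change. All dates needed are already collected.
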